Study visits are divided into five phases as detailed below.

Phase 1 – Screening/Consent: The Screening/Consent Phase will be completed virtually or in-person in 1-2 visits depending on scheduling and will take a total of about 1 to 2 hours. During this phase, the participant will be asked to do the following:

- Discuss details of the study with study staff and review/sign the consent form
- Provide contact information
- Review medical history
- Complete Mental Health Screening Questionnaire

Phase 2 – Initial Testing: The Initial Testing Phase involves one in-person visit and will take a total of about 2.5 hours. During this phase, the participant will be asked to do the following:

Qualitative Interview – Participants will complete a qualitative interview assessing factors and triggers influencing current physical activity participation. These sessions will be recorded as audio files for future reference by study staff.

- Measure height and weight
- Review medications
- Complete Paffenbarger Physical Activity Questionnaire
- Senior Fitness Test – Participants will perform a chair stand test, arm curl test, chair sit and reach test, back scratch test, 8-foot up and go test, and step-in-place test.
- Dispense Garmin activity monitor

Phase 3 – Randomization: Upon completion of the Screening/Consent and Initial Testing phases, participants will be randomized to one of two groups:

- Targeted Health Coaching (THC) Group – ~50% of study participants will be in the THC group.
- Standard Care (SC) Group – ~50% of study participants will be in the SC group.

Phase 4 – Intervention: The Intervention Phase will last about 3 months and will be different for the THC and SC groups:

- THC Group – Participants in the THC group will receive an exercise prescription (steps/day) based on their last cardiac rehabilitation session exercise prescription. Participants will be provided a Garmin wearable device to track steps/day. Additionally, participants will partake in 6 virtual or in-person health coaching sessions lasting approximately 30-60 minutes in duration. These sessions will take place approximately every other week during the 3-month intervention period.

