- To inform the health coach what the current barriers and triggers influencing the participant's ability to perform physical activity after structured CR. This will be discussed with the participants randomized to the THC group in their initial health coaching session.
- Develop the common themes of factors and triggers reported in this population. We will conduct a thematic analysis utilizing the baseline qualitative interview transcripts and two personnel. The personnel assigned for thematic interpretation will follow a step-by-step process: 1) familiarization with the transcript data; 2) develop an initial set of codes representing observed data meanings and patterns; 3) collate data excerpts by code; 4) group codes into potential themes; 5) review and revise themes with co-transcribing personnel. From this, we will assess the most common baseline self-reported factors and triggers influencing PA participation. Analyses will be focused on descriptive data including frequencies of the common themes identified.

For Aim 2, our statistical approach will be as follows:

We will classify maintenance in two ways – 1) using mean steps/day over the 3-month intervention period; and 2) calculated as (steps/day completed) divided by (steps/day prescribed) times 100 and average this metric over the 3-month study period. Data will be analyzed using Intent-to-Treat and statistical significance will be set at 0.05. We will assess the following:

Primary outcome: Within-group differences in maintenance metrics and Senior Fitness test scores (THC group n=13 vs. SC group n=13). Using 80% power at alpha level 0.05, we should be able to detect an effect size around 0.62 for analyses of pre-to-post change scores using steps per day as the primary outcome using paired t-tests, paralleling published findings.

Secondary outcome: Between-group differences in maintenance metrics and Senior Fitness Test scores (13 vs. 13)

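### The powered paired test on steps/day has no defined pre value, and its detectable effect of 0.62 cannot be reproduced from the stated inputs

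*Combined protocol and SAP*

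**What the plan says.** All of the analysis text is in Data Analysis & Statistical Considerations, under Aim 2.

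- **Metrics.** Maintenance is classified in two ways. The first is "using mean steps/day over the 3-month intervention period". The second is steps completed as a percentage of steps prescribed, with the instruction to "average this metric over the 3-month study period".
- **Primary outcome.** It covers within-group differences in both maintenance metrics and in the Senior Fitness Test scores, with 13 participants in each group.
- **Power.** At 80% power and alpha 0.05, "we should be able to detect an effect size around 0.62" for "pre-to-post change scores using steps per day as the primary outcome using paired t-tests". The basis offered is agreement with published findings. Sidedness, standardiser and pre-post correlation are not given.
- **Secondary outcome.** The same measures are compared between groups, 13 against 13.

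Study Procedures supplies the timing. Phase 2 (Initial Testing) includes "Dispense Garmin activity monitor". Phase 3 then says: "Upon completion of the Screening/Consent and Initial Testing phases, participants will be randomized to one of two groups". The steps/day prescription appears under Phase 4 for both arms and is derived from what was prescribed at the final CR session. Phase 6 repeats the Phase 2 tests apart from the interview and adds no step-count window.

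**The concern.** A paired t-test needs two values per participant. Each step metric, as defined, yields one: an average over the whole intervention. That average could serve as the post value, but nothing in the plan supplies the pre value. This affects both step metrics, including steps/day, the only outcome named in the power statement.

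Steps walked before randomisation that are not recorded cannot be recovered later. If the gap is left to the analyst, the estimate will depend on which days are chosen as baseline after the data are in. The plan says that the pilot's data will feed effect sizes and power for later studies. Without a pre value it cannot supply a within-group effect for steps/day.

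The power sentence raises a second, separate problem. A reader planning the next trial would take 0.62 as what 13 pairs can detect, and the stated inputs do not lead to that number.

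**Working it through.** **Part 1: is there a pre value for steps/day?** Each candidate in the documents:

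| Candidate | What the documents give | Serves as pre steps/day? |
|---|---|---|
| Garmin, Phase 2 | Dispensed at Initial Testing; no wear period, window or valid-day rule | Possible, not defined |
| Prescribed steps/day, Phase 4 | A target, and already the denominator of the second metric | No, not measured activity |
| Paffenbarger questionnaire, Phases 2 and 6 | Paired activity measure, not linked to the step metrics | No, not the Garmin steps/day that the metrics use |
| Early against late intervention weeks | Not mentioned; metrics are whole-period averages | No |

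The Senior Fitness Test is done in Phases 2 and 6, so its pre and post values are defined. The between-group comparison of three-month averages needs no pre value.

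**Part 2: the figure of 0.62.** Inputs from the Aim 2 text: paired t-test, n = 13 per group, alpha 0.05, power 80%. Assumption: the effect is in SDs of change, the natural reading for change scores. Sidedness is not stated, so both are shown.

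Formula: the test statistic is noncentral t with n − 1 degrees of freedom and noncentrality d√n. The detectable d is the value at which power equals 80%.

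*Attempt to reproduce 0.62 at n = 13:*

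- Noncentral t, two-sided: d = 0.847. Noncentrality is 0.847 × √13 = 3.05.
- Noncentral t, one-sided: d = 0.732.
- Normal approximation, two-sided: (1.960 + 0.842)/√13 = 2.802/3.606 = 0.777.
- Normal approximation, one-sided: (1.645 + 0.842)/√13 = 2.487/3.606 = 0.690.

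None gives 0.62. At d = 0.62 the noncentrality is 0.62 × 3.606 = 2.24, and power is 53.8% two-sided or 67.8% one-sided.

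*What would give about 0.62?* Noncentral t, two-sided:

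| Setting | Detectable d | Power at 0.62 |
|---|---|---|
| 22 pairs | 0.626 | 79.2% |
| 23 pairs | 0.611 | 81.1% |
| 26 pairs, arms pooled | 0.572 | 85.9% |
| 13 vs 13, two-sample (noncentrality d√(n/2)) | 1.145 | 32.9% |

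The two-sample d is in SDs of the three-month average, so it is not on the same scale as the paired d.

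*If 0.62 is instead in raw-score SDs*, with equal pre and post SDs and pre-post correlation r, then d in raw SDs = 0.847 × √(2(1 − r)) at n = 13, two-sided:

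| Assumed r | 0.3 | 0.5 | 0.6 | 0.7 | 0.8 |
|---|---|---|---|---|---|
| Detectable, raw SDs | 1.002 | 0.847 | 0.757 | 0.656 | 0.535 |

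Setting the result to 0.62 gives r = 1 − (0.62/0.847)²/2 = 0.73. The same step one-sided, with 0.732, gives r = 0.64. The documents give no correlation, so these values are assumptions.

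**The case against.** **The gap is underspecification, not impossibility.** The monitor is in participants' hands before randomisation, and the exclusion criteria refer to a five-month study period against about three months of intervention. Baseline wear is therefore feasible and nothing excludes it. This stands as far as it goes, but feasibility does not supply a definition.

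**The figure of 0.62 may be right.** A reader might infer that it is simply an error that overstates what 13 pairs can detect. The documents do not support that: with a raw-SD standardiser and a correlation near 0.73 it is correct at n = 13, two-sided, and the plan points to published findings that may lie behind it. What stands is that the figure cannot be reproduced from what is stated.

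**The power sentence does not set the sample size.** The plan ties the number randomised to pilot status. This stands. Correcting 0.62 changes no enrolment figure, and the low power of a pilot is not itself a fault.

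**Percent of prescribed steps is not a second kind of gap.** A reader might infer that a baseline could not be scored because the prescription appears only under the intervention phase. But the target derives from the last CR session, and no text describes it changing, so any baseline steps can be divided by it. The only thing missing is the baseline steps.

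**An activity measure is already paired.** The Paffenbarger questionnaire is collected at both visits. It is not steps/day and does not rescue the powered test.

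**Conclusion.** The point holds in two parts. First, neither step metric has a defined pre value, so the one analysis with a power statement cannot be carried out from the text as it stands. This needs to be fixed before data are analysed, and for baseline capture before further participants are randomised.

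Second, 0.62 is not what the stated inputs give. In SDs of change, 13 pairs detect about 0.85 two-sided (0.73 one-sided), and power at 0.62 is about 54% (68%). This part rests on the effect being in SDs of change. Two-sided, 0.62 would hold on an unstated raw-SD scale with correlation about 0.73, or in SDs of change with about 22 to 23 pairs. The latter would match pooled arms after losing 12% to 15% of 26 (1 − 23/26 and 1 − 22/26), but no dropout rate is stated and the primary comparison is within each group. Taken alone, this part is a correction to the text.

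A reader might also infer that the whole primary outcome fails. It does not: the Senior Fitness Test scores have both visits, and the between-group comparisons stand.

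**What to change.** **1. Power sentence, in any case.** Restate the detectable effect for the chosen test: about 0.85 SD of change (paired, n = 13, two-sided) or about 1.15 SD (13 vs 13, two-sided). Alternatively keep 0.62 and state the standardiser, correlation, sidedness or number of pairs behind it. The cost is a rewritten sentence.

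**2. Step metrics: choose one option and state it.**

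(a) *Define the baseline.* Set a pre-randomisation Garmin window, for example about 7 days after dispensing with a minimum number of valid days, as the pre value, and name the three-month mean as post. The same baseline steps divided by prescribed steps/day give a pre value for the percentage metric. No extra device is needed. Costs: about a week's delay to randomisation; a new device may itself raise activity; because people may be approached during CR or after it, the window may fall during CR for some and after it for others; and it cannot be applied to anyone already randomised without baseline wear.

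(b) *Drop the paired test for the two step metrics.* State explicitly that the between-group comparison of three-month averages, now listed as secondary, becomes their primary analysis. This needs no new data and fits Aim 2, which is to compare coaching with standard care. Costs: the primary analysis for these metrics changes, and the within-group steps/day result is lost.

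Under either option the paired Senior Fitness Test analysis stays as planned.
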